1.1. Study Objectives

1.1.1. Primary Objectives

- To evaluate safety of ENTO in combination with VCR and dexamethasone in adult subjects with previously treated relapsed or refractory B-cell lineage ALL

1.1.2. Secondary Objectives

- To determine the recommended dose of ENTO in combination with VCR and dexamethasone in adult subjects with previously treated relapsed or refractory B-cell lineage ALL
- To evaluate the therapeutic response of ENTO in combination with VCR and dexamethasone in adult subjects with previously treated relapsed or refractory B-cell lineage ALL

1.1.3. Exploratory Objectives

PPD [REDACTED]

[REDACTED]

[REDACTED]

PPD [Redacted]

[Redacted]

[Redacted]

1.2. Study Design

This is an open-label, Phase 1b dose-escalation and Phase 2 expansion study evaluating the safety, efficacy, tolerability, and PK of ENTO in combination with VCR and dexamethasone.

The study was originally designed for 2 stages sequentially: (1) Phase 1b dose escalation; (2) Phase 2 expansion. However, due to the low response rate to ENTO in combination with VCR and dexamethasone in Phase 1b portion, per the Sponsor’s decision, it has been decided not to proceed with the dose expansion (ie, Phase 2) portion of this study.

There are four dose levels in the dose escalation phase (Table 1-1) where subjects in cohorts of 3 to 6 are sequentially enrolled into one of the dose levels using a 3+3 dose escalation design (Table 1-2). The starting dose level for the first cohort is defined as Dose Level 1.

Table 1-1 Entospletinib/Vincristine Dose Escalation

Dose Level	Entospletinib (ENTO)	Vincristine (VCR)
1	200 mg BID	0.5 mg per dose
2	400 mg BID	0.5 mg per dose
3	400 mg BID	1 mg per dose
4	400 mg BID	2 mg per dose

BID = twice per day

Dose Escalation: Induction (Lead-in, Cycle 1 and Cycle 2)

Lead-in (ENTO Monotherapy): Beginning on Day -7 of Lead-In, ENTO will be administered orally twice daily (BID) for 7 days as a single agent.

Cycle 1 and Cycle 2 (ENTO, VCR, dexamethasone, CNS prophylaxis)

[figure not shown]
ENTO will be continuously administered orally BID in combination with chemotherapy for the duration of the study treatment.

VCR will be administered on Days 1, 8, 15 and 22 of each 28-day cycle for Cycle 1 and 2 only.

Dexamethasone (20 mg twice daily for 4 days) will be administered orally during Cycle 1 on Days 8-11 and Days 22-25 and during Cycle 2 on Days 1-4 and Days 15-18.

CNS prophylaxis per institutional standard will be given on Day 28 (± 3 days) of Cycle 1 and Cycle 2.

Dose Escalation treatment schedule is outlined in the schema below:

Bone marrow (BM) aspirate/biopsy will be performed during screening (within 28 days prior to the start of study treatment), Cycle 1 on Day 8 and during both Cycle 1 and Cycle 2 on Day 28.

Imaging (computerized tomography [CT] with contrast or Positron Emission Tomography (PET) scan should be performed for subjects with extramedullary disease (EMD) if these are the only sites of evaluable disease (no BM involvement) to evaluate disease status and response, at screening, Cycle 1 Day 8 and Day 28, and Cycle 2 Day 28. Imaging will be evaluated using the NCCN guidelines version 2.2016 (Patients with no BM involvement and only EMD will not require BM aspirate/biopsy on cycle 1 day 8 and day 28, and cycle 2 day 28).

Up to 6 subjects will be dosed per dose level. Dose escalation will be performed based on assessments of Dose Limiting Toxicities (DLTs) and other adverse events data obtained within the DLT window (ENTO Lead-in and Cycle 1; study day 1 through day 35). Subjects with complete remission (CR), morphologic CR with incomplete blood count recovery (CRi), or partial remission (PR) on Day 28 of Cycle 1 bone marrow, and /or subjects who in the investigator's opinion have obtained clinical benefit from Cycle 1 induction, will continue to Cycle 2 of induction.

During the DLT assessment window, subjects who fail to complete 21 days of GS-9973 or fail to receive sufficient exposure ($> 50\%$ of planned total dose) to VCR and dexamethasone for reasons other than treatment-related toxicity will not be evaluable for DLT assessment and an additional (replacement) subjects may be enrolled to that dose level in order to provide adequate safety data for dose escalation decisions.

Decision to open the next higher dose level to enrollment or expand the current cohort will be determined by the sponsor in consultation with study Principal Investigators (PIs).

The maximum tolerated dose (MTD) is defined as the highest tested dose associated with an observed DLT rate of < 33% during the DLT window. A minimum of 6 subjects need to be treated at a dose level before this dose level can be determined as MTD or recommended dose.

Table 1-2 Dose Escalation/DLT Guidelines

Number of subjects with DLT at a given level	Escalation Decision Rule
0 out of 3	Enroll 3 subjects at the next higher dose level. If this dose level is the highest dose level, it will be declared the maximally administered dose, and enroll 3 additional subjects at this dose level.
1 out of 3	Enter 3 additional subjects at this dose level. If 0 of these 3 subjects experience DLT, proceed to the next higher dose level. If 1 or more of them experience DLT, then dose escalation is stopped, and this dose is declared the maximally administered dose. Three additional subjects will be entered at the next lower dose level if only 3 subjects were treated previously at that dose.
≥ 2 out of 3	Dose escalation will be stopped. This dose level will be declared the maximally administered dose (highest dose administered). Three additional subjects will be entered at the next lower dose level if only 3 subjects were treated previously at that dose.
≤ 1 out of 6 at highest dose level below the maximally administered dose	This is the maximum tolerated dose (MTD) and generally the recommended dose. At least 6 subjects must be enrolled at MTD or the recommended dose.

Maintenance:

It is anticipated that most subjects who are transplant eligible will receive hematopoietic stem cell transplant (HSCT) therapy with curative intent if a CR is reached. In the absence of a suitable alternative therapeutic option, subjects who obtain clinical benefit (at least PR) after completing both cycles of induction therapy in dose escalation may continue ENTO at the assigned dose level during maintenance for up to 36 cycles. Subjects will continue ENTO and VCR at their assigned dose. ENTO will continue to be taken orally twice daily with VCR to be administered on Day 1 of each 28-day cycle and dexamethasone 20 mg total dose daily (either a divided dose of 10 mg twice daily or a single dose of 20 mg once daily) on Days 1-4 and Days 15-18 of each 28-day cycle.

Bone marrow evaluations and additional central nervous system (CNS) directed therapy can be performed as clinically indicated during maintenance.

1.3. Sample Size and Power

The study implements 3+3 design. Sequential dose-escalation is consistent with usual oncologic paradigms for dose ranging. The intent is to limit the number of subjects who are exposed to excessively toxic doses of a drug in an early phase evaluation of an anticancer agent. The trial employs the standard National Cancer Institute (NCI) definition of MTD (starting dose associated with DLT in < 33.3% of subjects during the DLT assessment window) to determine

dose escalation. The cohort size and dose-escalation rules establish a low probability of increasing the dose if the true rate of DLT is high while there is a high likelihood of escalating or proceeding to the next cohort of the study if the true underlying probability of DLT is low. [Table 1-3](#) shows the probability of escalating to the next dose level or proceeding to the next stage, based on the true rate of DLT at the current dose level. If the true underlying probability of DLT is low (eg, < 10%) at the current dose level, there is a high probability (> 0.91) of dose escalation to the next dose level. Conversely, if the true underlying proportion of DLT is high (eg, > 60%) at the current dose level, there is a low probability (< 0.08) of escalation to the next dose level.

Table 1-3 Probability of Dose Escalation (N=3+3)

True Incidence of DLT	Probability of Escalating
10%	0.91
20%	0.71
30%	0.49
40%	0.31
50%	0.17
60%	0.08

Assuming that 4 planned dose levels are tested for escalation and 3, 3, 6 and 6 subjects are tested at each dose level, respectively (18 subjects for escalation), and assuming 10% subjects are not evaluable during dose escalation, 20 subjects will be enrolled during dose escalation.

2. TYPE OF PLANNED ANALYSIS

2.1. Interim Analysis

No formal interim analyses are planned in this study. The GSI study team and the investigators will collectively discuss study conduct and accumulating safety and other data.

2.2. Final Analysis

Final study reporting is expected to occur after all subjects have discontinued the study.

3. GENERAL CONSIDERATIONS FOR DATA ANALYSES

Analysis results will be presented using descriptive statistics. For categorical variables, the number and percentage of subjects in each category will be presented; for continuous variables, the number of subjects (n), mean, standard deviation (StD) or standard error (SE), median, first quartile (Q1), third quartile (Q3), minimum, and maximum will be presented.

By-subject listings will be presented for all subjects in the Full Analysis Set and sorted by subject identification (ID) number, visit date, and time (if applicable). Data collected on log forms, such as AEs, will be presented in chronological order within the subject. The treatment group to which subjects are initially assigned will be used in the listings. Age, sex at birth, race, and ethnicity will be included in the listings, as space permits.

3.1. Analysis Sets

Analysis sets define the subjects to be included in an analysis. The analysis set will be identified and included as a subtitle of each table, figure, and listing.

3.1.1. All Enrolled Analysis Set

The All Enrolled Analysis Set includes all subjects who receive a study identification number in the study after screening.

3.1.2. Full Analysis Set

The Full Analysis Set (FAS) includes all subjects who receive at least 1 dose of study treatment.

This analysis set will be used in the analyses of subject characteristics and efficacy.

3.1.3. Safety Analysis Set

The Safety Analysis Set includes all subjects who receive at least 1 dose of study treatment.

This analysis set will be used in the drug exposure and safety analyses.

3.1.4. Dose-Limiting Toxicity Analysis Set

Dose-Limiting Toxicity (DLT) Analysis Set includes all subjects in the Safety Analysis Set who meet at least one of the following criteria:

- Receive at least 21 days of ENTO, >50% of planned total dose of VCR and dexamethasone during the DLT assessment window (refer to Section 1.2)
- Experience a DLT during the DLT assessment window

This analysis set will be used for analyses related to DLT.

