3.3.1. Dose Escalation

During dose escalation, there will be four dose levels (outlined in Table 3-1) investigated in dose escalation where subjects in cohorts of 3 to 6 will sequentially enroll into one of the dose levels using the 3+3 dose escalation design. The starting dose level for the first cohort is defined as Dose Level 1.

Dose Level	G8-9973	Vincristine (VCR)
1	200 mg BID	0.5 mg per dose
2	400 mg BID	0.5 mg per dose
3	400 mg BID	1 mg per dose
4	400 mg BID	2 mg per dose

Table 3-1.GS-9973/VCR Dose Escalation

Subjects in Dose Level 1 will receive 200 mg GS-9973 taken orally twice daily (BID). Subjects in Dose levels 2 to 4 will receive 400 mg GS-9973 orally BID. Subjects in all dose levels will receive dexamethasone 20 mg BID for four days during Cycle 1 on Days 8-11 and Days 22-25 and during Cycle 2 on Days 1-4 and Days 15-18. Each treatment cycle is 28 days in length.

In the absence of toxicity requiring a drug interruption (as defined in Section 3.5.2.1), dosing of GS-9973 will be taken continuously without interruption.

Subjects will have evaluations for safety and provide blood for drug levels prior to starting Lead-in and 1.5 hours after the first dose of GS-9973.

Additional PK blood samples will be collected at (applies to both escalation and expansion):

- Pre-dose during Cycle 1 on Day 1 and 1.5 hours (± 30 minutes) post-dose of GS-9973
- Pre-dose during Cycle 1 on Day 8, and 1.5 hours (± 30 minutes) post-dose of GS-9973
- Pre-dose during Cycle 1 on Day 28 and Cycle 2 on Day 28, and 1.5 hour (± 30 minutes) post-dose of GS-9973
- A sample of cerebrospinal fluid (CSF) for PK analysis will be taken during Cycle 1 on Day 28 and Cycle 2 on Day 28 (untimed sample) prior to CNS prophylaxis administration

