3.3.1.1. Treatment Plan in Dose Escalation

Subjects will be enrolled and dosed in accordance with the 3+3 dose escalation design (Table 3-1). Intra-subject dose escalation is not allowed. Up to 6 subjects will be dosed per dose level. Dose escalation will be performed based on assessments of DLTs and other adverse events data obtained within the DLT window (GS-9973 Lead-in and Cycle 1; study day 1 through day 35). Subjects with CR, CRi, or PR on Day 28 of Cycle 1 bone marrow, and /or subjects who in the investigator's opinion have obtained clinical benefit from Cycle 1 induction, will continue to Cycle 2 of induction.

During the DLT assessment window, subjects who fail to complete 21 days of GS-9973 or fail to receive sufficient exposure (> 50% of planned total dose) to VCR and dexamethasone for reasons other than treatment-related toxicity will not be evaluable for DLT assessment and an additional (replacement) subjects may be enrolled to that dose level in order to provide adequate safety data for dose escalation decisions.

Decision to open the next higher dose level to enrollment or expand the current cohort will be determined by the sponsor in consultation with study Principal Investigators (PIs).

The maximum tolerated dose (MTD) is defined as the highest tested dose associated with an observed DLT rate of < 33% during the DLT window.

A minimum of 6 subjects need to be treated at a dose level before this dose level can be determined as MTD or recommended dose.

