3.5. Dose-Limiting Toxicity

The evaluation period for dose-limiting toxicity (DLT) will occur from the start of treatment through the end of Cycle 1 in the escalation phase. Subjects who fail to complete 21 days of GS-9973 or fail to receive sufficient exposure (> 50% of planned total dose) to VCR and dexamethasone for reasons other than treatment-related toxicity will be considered not evaluable for DLT assessment and additional (replacement) subjects may be enrolled to that dose level in order to provide adequate safety data on which to base dose escalation decisions. All toxicities will be graded using National Cancer Institute (NCI) Common Terminology Criteria for Adverse Events (CTCAE) Version 4.03 (Appendix 3).

The occurrence of any of the following toxicities during Lead-in/Cycle 1 will be considered a DLT if judged by the Investigator to be possibly, probably, or definitely related to the administration of any drug in the treatment regimen (GS-9973, VCR, dexamethasone, institutional standard CNS prophylaxis):

- Grade 4 (or higher) non-hematologic toxicity
- Grade 3 non-hematologic toxicity lasting \geq 7 days despite optimal supportive care
- Any Grade 3 non-hematologic laboratory value if:
 - Medical intervention is required to treat the patient, or
 - The abnormality leads to hospitalization, or
 - The abnormality persists for >1 week

- Grade 4 Neutropenia (ANC < 500 /µl) persistent for greater than 14 days or associated with febrile neutropenia
- Grade 4 thrombocytopenia (platelets < 25,000/µl) persisting for greater than 14 days (or greater than 25,000 /µl, but requiring prophylactic platelet transfusion to maintain this level)

The following will NOT be considered as a DLT for the purposes of this study, regardless of grade:

- Alopecia
- Fatigue
- Nausea or vomiting controllable with anti-emetic therapy
- Catheter-associated venous thrombosis
- Infection (or infection-related toxicities such as fever/sepsis, unless it is felt that the infection resulted from unexpectedly complicated myelosuppression due to study medication)
- Transient electrolyte abnormalities (any grade) that are not clinically significant and are correctable within 24 hours
- Transient liver function test abnormalities (AST, ALT, bilirubin, or alkaline phosphatase) that resolve to \leq Grade 2 within 7 days

Number of subjects with DLT at a given level	Escalation Decision Rule	

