3.5.2. Guidelines for Dose Modifications

3.5.2.1. Dosing Delays/Dose Modifications Attributed to GS-9973 (beyond Cycle 1)

If the following signs or symptoms are medically manageable, they are not to be a consideration with respect to the subject's dosing or continuation on study: nausea/mild vomiting/diarrhea, drug-related fever or chills, transient and correctable laboratory test abnormalities, line associated thrombosis, or alopecia. See Appendix 3.

There will be no dose modifications during Lead-in or Cycle 1 for GS-9973, VCR, or dexamethasone. Subjects experiencing toxicity attributed to these agents during Cycle 1 requiring discontinuation of any drug shall be removed from study and will be considered a DLT.

Dose modification of GS-9973 in subsequent cycles is permitted following guidelines provided in Appendix 3. Subjects who experience a non-hematologic toxicity assessed as GS-9973 related that is Grade 3 or higher will hold dosing of GS-9973 until the toxicity resolves to \leq Grade 1, and then may resume study therapy at the prior dose through the end of the cycle (or decreased by 1 dose level after discussion with Sponsor). For subjects assigned to Dose Level 1, the decreased dose of GS-9973 will be defined as 100 mg orally twice daily. Missed doses are not to be made up.

Adverse events and laboratory abnormalities will be graded using the CTCAE, Version 4.03.

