8.2.3. DLT Analysis Set

The DLT Analysis Set includes subjects in FAS with sufficient drug exposure (Section 3.3.1) or experience a DLT during the DLT assessment window. Subjects will be grouped by dose level and overall.

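### The SAP drops the protocol's DLT rate with 90% CI yet declares no deviations, and the DLT definition and denominator behind that rate need to be settled

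*SAP*

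**What the plan says.** **Planned analysis.** Protocol 8.1.2 makes DLT occurrence the primary endpoint. Protocol 8.6.2 calls for DLTs to be listed and also summarised, as a rate for each dose level with a 90% CI. SAP 7.1.7 uses the DLT analysis set but specifies only a listing of DLT events. The AE summaries in SAP 7.1.6.1 contain no DLT entry. SAP 7.7 says that nothing departs from the protocol's safety analyses.

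**What counts as a DLT.** Protocol 3.5 gives a list with grade and duration thresholds, opening with "The occurrence of any of the following toxicities during Lead-in/Cycle 1 will be considered a DLT if judged by the Investigator". It adds a second list of events (among them fatigue, alopecia and most infections) that are not to "be considered as a DLT for the purposes of this study, regardless of grade". Stopping a drug is on neither list. Protocol 3.5.2.1 says that subjects with "toxicity attributed to these agents during Cycle 1 requiring discontinuation of any drug shall be removed from study and will be considered a DLT", and sets no grade or duration.

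**Who is in the denominator.** SAP 1.2 and Protocol 3.3.1.1 both say that under-exposed subjects "for reasons other than treatment-related toxicity will not be evaluable for DLT assessment", so a shortfall caused by treatment-related toxicity does not make a subject non-evaluable. SAP 3.1.4 admits subjects who "Receive at least 21 days of ENTO, >50% of planned total dose of VCR and dexamethasone during the DLT assessment window", or who have a DLT in the window. Protocol 8.2.3 has the same two-part form: the set "includes subjects in FAS with sufficient drug exposure (Section 3.3.1) or experience a DLT during the DLT assessment window". Neither set definition writes out the toxicity exception.

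**The concern.** The primary endpoint loses its only planned estimate, and the SAP section meant to record such a change says there is none. A reader of the report would see a list of DLTs, possibly empty, with no statement of how little 3 to 6 subjects per level can rule out.

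Protocol 3.3.2 reports no DLTs in Phase 1 but does not say whether that count applied the 3.5 lists alone or also the discontinuation rule in 3.5.2.1. At these cohort sizes one subject moves both the count and the denominator. A restored rate is therefore interpretable only if the DLT rule and the treatment of early toxicity stops are stated.

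**Working it through.** **The plan's own figures.** Under the 3+3 rule, P(escalate) = (1−p)³ + 3p(1−p)² × (1−p)³. For p = 10, 20, 30, 40, 50 and 60% this gives 0.9061, 0.7086, 0.4943, 0.3093, 0.1719 and 0.0824, which round to Protocol Table 8-1 and SAP Table 1-3. Enrolment is 18/(1 − 0.10) = 20, as stated. The design arithmetic stands; the problem is in definitions and reporting.

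**Step 1: planned against specified output.**

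| Item | Protocol 8.6.2 | SAP 7.1.7 and 7.1.6.1 |
|---|---|---|
| Listing of DLTs | yes | yes |
| DLT rate by dose level | yes | no |
| 90% CI | yes | no |
| Omission recorded in SAP 7.7 | – | no |

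**Step 2: what the missing interval would show.** Inputs: zero DLTs (Protocol 3.3.2); cohorts of 3 or 6 (Protocol Table 3-2); exact binomial method (Protocol 8.3 names it for 95% intervals; I assume it carries over to 90%). With zero events the two-sided 90% upper limit is 1 − 0.05^(1/n).

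- n = 6: 1 − 0.607 = 39.3%
- n = 3: 1 − 0.368 = 63.2%

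Both exceed the 33% in the MTD definition (Protocol 3.3.1.1). That threshold applies to the observed rate, so 0/6 still satisfies it. The comparison shows only how much uncertainty a bare listing leaves unstated.

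**Step 3: the two DLT rules side by side.**

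| Attributed toxicity that stops a drug | Under 3.5 | Under 3.5.2.1 |
|---|---|---|
| Cycle 1, event on the never-a-DLT list (e.g. fatigue) | not a DLT | DLT |
| Cycle 1, event on neither list (e.g. Grade 3 non-laboratory toxicity under 7 days) | not listed | DLT |
| Lead-in, event not on the DLT list | not a DLT | silent |

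Row 1 is a direct contradiction. In row 2 it is unclear whether 3.5.2.1 adds a criterion to the 3.5 list. In row 3 only 3.5 speaks.

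**Step 4: size of the effect.** Suppose a dose level has no listed DLT and one subject who stops early for toxicity before meeting the SAP 3.1.4 exposure criterion. Such a subject is an assumption; the documents report none. The lower limit for one event is 1 − 0.95^(1/n); the upper limit is the 95th percentile of Beta(2, n−1).

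| Handling | 6 treated (90% CI) | 3 treated (90% CI) |
|---|---|---|
| Counted as a DLT | 1/6 = 16.7% (0.9–58.2%) | 1/3 = 33.3% (1.7–86.5%) |
| Kept, not a DLT | 0/6 (0–39.3%) | 0/3 (0–63.2%) |
| Dropped from the set | 0/5 (0–45.1%) | 0/2 (0–77.6%) |

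The first two rows differ by the DLT definition (Protocol 3.5 against 3.5.2.1). The last two differ by whether SAP 3.1.4 carries the exception in SAP 1.2.

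**The case against.** **On the missing rate.** The SAP supports a synoptic report of Phase 1b only, no DLTs were reported, and a reader could rebuild the rate from the DLT listing and the DLT-set counts by dose level in SAP 4.1. This lowers the cost of the omission. It does not make the statement in SAP 7.7 correct.

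**On the DLT definition.** The 3.5 list does not say that only its items are DLTs, so 3.5.2.1 may simply add one. The first paragraph of 3.5.2.1 also says that several events, if medically manageable, should not affect dosing or continuation: nausea and mild vomiting, diarrhoea, drug-related fever or chills, transient laboratory changes, line thrombosis and alopecia. These largely overlap the 3.5 exclusions. Both points stand, and they narrow the direct contradiction mainly to fatigue and infection. A reader might also infer that an unlisted Lead-in stop falls under no rule. It does not: 3.5 covers the Lead-in, and such a stop is not a DLT there.

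**On SAP 3.1.4.** It follows the structure of Protocol 8.2.3, whose pointer to Section 3.3.1 may bring in the exception. SAP 3.1.4 has its own reference to Section 1.2, but that follows the mention of the assessment window, so whether it imports the exception is open. While the SAP plans only a listing of DLTs, set membership changes little beyond the SAP 4.1 count. This part is therefore a wording alignment that matters once the rate is restored.

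**A tempting stronger reading.** The protocol gives "dexamethasone 20 mg BID for four days during Cycle 1 on Days 8-11 and Days 22-25". That is 2 × 4 × 40 mg = 320 mg, and the first course is 160 mg, exactly half. If the over-50% rule applies to each drug separately, nobody can meet it before study day 29, after 28/35 = 80% of the window. One might infer that SAP 3.1.4 wrongly loses most early stops. The documents do not support that. The figure counts days, not subjects; it follows from the protocol's own exposure rule; and early stops for non-toxicity reasons are meant to be excluded.

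**Conclusion.** The main point holds. The SAP omits the protocol's rate and 90% CI for the primary endpoint and declares no deviation. With zero DLTs, what goes unreported is an upper limit of 39.3% at six subjects or 63.2% at three, assuming exact intervals.

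The second point holds in a narrower form. Protocol 3.5 and 3.5.2.1 contradict each other for events on the never-a-DLT list that force a Cycle 1 stop, and their relation is unclear for other unlisted toxicities. One such subject among six would be the difference between 16.7% and 0%. The SAP 3.1.4 wording is minor and shifts the upper limit between 45.1% and 39.3% in the same example.

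A reader might infer that SAP 3.1.4 by itself understates toxicity, or that escalation decisions were compromised. Neither follows. If 3.5.2.1 governs, a Cycle 1 toxicity stop is a DLT and enters the set as such; if 3.5 governs, dropping a non-DLT subject raises the rate or leaves it at zero. Protocol 3.3 says escalation was already complete, and the SAP was signed in January 2019, so these are effects on reporting. Whether any such subject exists is unknown, although SAP 4.1 and 7.1.6.1 would make one traceable.

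**What to change.** 1. In SAP 7.1.7, restore the DLT rate by dose level with an exact 90% CI. Otherwise record and explain its omission in SAP 7.7.
2. Reconcile Protocol 3.5 with 3.5.2.1, without presupposing which governs, and include Lead-in stops. State in the SAP which rule produced the reported count.
3. Check the existing Lead-in and Cycle 1 discontinuations. If any was for toxicity, show the rate with and without it counted.
4. State in SAP 3.1.4 that subjects under-exposed because of treatment-related toxicity stay in the DLT set, in line with SAP 1.2.

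The cost is some SAP wording, one small table and a check of data already planned for output: reasons for stopping each drug, DLT-set membership, and AEs leading to discontinuation. SAP Section 1 already provides for changes after finalisation to be documented in the study report. The downside is that the reported rate or upper limit may move in either direction: up if a stop is counted as a DLT, down if a non-DLT subject is kept in the denominator.
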